### Evaluation of COVID-19 effects on AEs

The direct effect of COVID-19 for AEs will be assessed via listings of COVID-19 related AEs. The following listings will be generated using the ‘COVID-19 related terms MedDRA 23.0 update Spreadsheet’ (<https://www.meddra.org/covid-19-related-terms-meddra-230-update-spreadsheet>, last accessed on 28 May 2020) as available from Maintenance and Support Services Organization (MSSO), considering all ‘search terms for COVID-19-related’ =’Y’. The following information will be provided:

- Subject ID, country, age, sex, race
- Date of first, last treatment with study drug
- COVID-19-associated AE start date (day), COVID-19 associated AE stop date (day)
- AE preferred term, verbatim
- Toxicity grade
- Seriousness
- Relationship to treatment
- Action taken
- Outcome

The indirect effect of COVID-19 for AEs will be assessed based on the difference in incidence rate between subgroups of pre and during COVID-19 period according to categorization method with time window:

- For common TEAEs applying frequency threshold of 10% in either subgroup of pre/during COVID-19 period, butterfly plots displaying incidence rates of TEAEs NCI-CTCAE severity grade  $\leq 2$  and  $\geq 3$  will be provided.
- For each AESIs defined in Section 15.2.4 occurred on 4 or more participants in any subgroup (Rule-of-4), forest plots displaying incidence rates, differences in incidence rates as well as the CI for the difference will be provided.

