M7824 has shown promising clinical efficacy signal in BTC patients progressing after platinum-based 1L treatment (Study MS200647-0008). Thirty Asian participants were treated with M7824 at dose of 1200 mg every 2 weeks. As of 20 March 2018, 30 participants who had previously received 1L treatment for BTC, received M7824 for a median duration of 8.9 weeks (range: 2 to 57.6 weeks); 5 participants remained on treatment at the time of data cutoff. Seven participants had a confirmed objective response (OR) by Investigator read (ORR 23.3%) and 6 participants had a confirmed OR by IRC (ORR 20%), including 1 confirmation of response after cutoff. Per anatomical location, the ORR was 14.3% (1 out of 7) in study participants with extrahepatic CCA and 40% (4 out of 10) in study participants with intrahepatic CCA, 16.6% (2 out of 12) in study participants with gallbladder carcinoma. No responses were observed in ampullary cancer (0 out of 1). With a minimum follow-up of 8 months, the duration of response (DOR) ranged from 0.7 to 6.9 months with 5 of 7 responses ongoing at the data cutoff date. Besides the confirmed ORR, 1 additional participant had an ongoing partial response (PR) for 7.6+ months after initial progression. The observed clinical efficacy, therefore, compares favorably to the calculated benchmark of existing 2L treatment options and there is a strong rationale with preclinical and clinical data to justify further clinical development of M7824 in 2L BTC, with the potential to establish M7824 as the standard of care.

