### 6.1 Primary and Second Analysis

Table 2 displays an overview of the primary and secondary analyses to be provided for this study.

**Table 2** Overview of Analyses

Analysis	Data cut-off point	Endpoints
Primary analysis (PA) at 9 Months	9 months after the first dose of the last of 141 planned participants	Full evaluation of all efficacy and safety endpoints. Plus, assessment of impact of COVID-19.
Second analysis at 15 Months	15 months after the first dose of the last of 141 planned participants	Full evaluation of all efficacy and safety endpoints

The timing of conduct of the primary and secondary analyses will be triggered by the data cut-off points displayed in Table 2 above and will evaluate all criteria described in this IAP.

CCI

## 7

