**Categorization of participants for COVID-19 impact assessment**

For the assessment of COVID-19 impact on this study, participants will be categorized as being affected by COVID-19 (either due to infection or due to circumstances of social distancing affecting the capabilities of sites/hospitals etc.) based on the COVID-19 study period defined as:

- The start of COVID-19 study period will be defined by country as the minimum of the date of the first death from COVID-19 occurred in each country according to the published data by European Centre for Disease Prevention and Control on 26th June 2020 and 11 March 2020 (WHO-start of world-wide pandemic).
- Post-pandemic could be defined as date (1) vaccination is released, (2) WHO declares COVID-19 pandemic over, (3) region-specific calls are made to end social distancing measures with no relevant rise in cases thereafter. As study treatment for the last participant started on 3rd January 2020, no participant will be grouped into the post COVID-19 study period for this study and no post-pandemic date will be defined.

Participants will be categorized into subgroups according to the methods shown in [Table 4](#) depending on the purpose of analysis.

**Table 4** Types of categorization for COVID-19 assessment

Type of categorization	Subgroup	Definition
Categorization for assessment on efficacy	Pre	Participant started treatment prior to and had progressive disease or died or withdrew from tumor assessments prior to COVID-19 study period
	During	Participant started treatment prior to or during COVID-19 study period and had any tumor assessments during the COVID-19 study period
	Post*	Participant started treatment post the COVID-19 study period
Categorization for assessment on safety without time window	Pre	Participant started treatment prior to COVID-19 study period
	During*	Participant started treatment during the COVID-19 study period
	Post*	Participant started treatment post the COVID-19 study period
Categorization for assessment on safety with time window	Pre	Participant started treatment 3 months prior to COVID-19 study period
	During	Participant started treatment on or after the date 3 months prior to COVID-19 study period
	Post*	Participant started treatment post the COVID-19 study period

\* No participants will be categorized into the 'post COVID-19 study period' or the 'during COVID-19 study period for safety without time window' for this study.

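### The comparison meant to show COVID-19's indirect effect on adverse events groups participants by treatment start date, not event date, so events are misclassified both ways and a real effect is attenuated

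*SAP*

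**What the plan says.** SAP 15.1.1 (Evaluation of COVID-19 effects on AEs) separates a direct effect, shown by listings of COVID-19-coded events, from an indirect effect. The indirect effect is to be "assessed based on the difference in incidence rate between subgroups of pre and during COVID-19 period", "according to categorization method with time window". The outputs are butterfly plots for common TEAEs, and forest plots for AESIs with rate differences and confidence intervals.

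Table 4 in SAP 9 defines the two groups for this method:

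- 'Pre': "Participant started treatment 3 months prior to COVID-19 study period". I read this as more than 3 months before, the complement of 'during'.
- 'During': "Participant started treatment on or after the date 3 months prior to COVID-19 study period".

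The COVID-19 period start is "defined by country as the minimum of the date of the first death from COVID-19 occurred in each country" and 11 March 2020, so 11 March is the latest it can be. SAP 9 also gives the end of accrual: "As study treatment for the last participant started on 3rd January 2020". The Table 4 footnote confirms that nobody started treatment inside the period.

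The on-treatment period in SAP 9 runs from first dose to last dose plus 30 days (plus 90 days for immune-related AEs), or to the day before subsequent anticancer therapy. It is not divided at the COVID-19 start. The efficacy rows of Table 4, by contrast, consider whether tumor assessments took place during the period.

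**The concern.** Whether an adverse event belongs to the pandemic depends on when it happened. Table 4 instead labels the whole participant by first-dose date, and every treatment-emergent event follows that label. Two errors result. An early starter still on drug in spring or summer 2020 contributes pandemic-time events to 'pre'. A late starter contributes all events from the weeks before the pandemic to 'during'. Both errors pull the groups together.

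This is the only analysis that the SAP assigns to the indirect effect. If the forest plots show little difference, a reader of the study report may take that as evidence that disrupted care did not change the safety profile. The comparison has little ability to show such a change.

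**Working it through.** The plan states no figure of its own here, so there is nothing to reproduce first.

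**Step 1: dates, for a country starting on 11 March 2020.**
- 'During' opens 3 months earlier, on 11 December 2019, and closes with the last first dose on 3 January 2020: 21 + 3 = 24 days of accrual.
- Time from first dose to the period start: 31 + 31 + 29 = 91 days for the earliest 'during' starter, and 28 + 29 + 11 = 68 days for the latest.
- The primary cut-off is "9 months after the first dose of the last of 141 planned participants", about 3 October 2020, which is 206 days after 11 March. Early starters still on treatment can therefore add many months of pandemic time to 'pre'.

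**Step 2: a participant with median treatment duration.** The protocol gives one duration figure, in 2.2 Background: 30 participants in the earlier second-line study "received M7824 for a median duration of 8.9 weeks". I use it as an assumption for this trial. 8.9 × 7 = 62.3 days. If that figure includes the 14 days after the last dose, as the SAP 13 formula does, the last dose falls at 62.3 − 14 = 48.3 days.

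| Window | Length (days) | Pre-pandemic share, latest to earliest 'during' starter |
|---|---|---|
| 62.3 + 30 | 92.3 | 68/92.3 = 74% to 91/92.3 = 99% |
| 48.3 + 30 | 78.3 | 68/78.3 = 87% to 100% |
| 62.3 + 90 (irAEs) | 152.3 | 68/152.3 = 45% to 91/152.3 = 60% |
| 48.3 + 90 (irAEs) | 138.3 | 68/138.3 = 49% to 91/138.3 = 66% |

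**Step 3: average over durations.** The median participant overstates the problem, because long-stayers supply most of the pandemic time. I therefore simulated on-treatment time (last dose plus 30 days, cut at 3 October 2020). Assumptions not in the documents: uniform accrual from 15 March or 1 June 2019 to 3 January 2020; one COVID-19 start date for all countries; a constant event hazard within each period. Treatment duration has median 8.9 weeks and is either exponential or Weibull with one sixth still treated at 8 months. The Weibull reflects the earlier study's 5 of 30 still on treatment, with minimum follow-up of 8 months. Country first-death dates are not given, so the start was varied from 15 January to 11 March 2020.

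| Quantity | Start 11 March | Start 15 January |
|---|---|---|
| 'During' participants, of 141 | 11–15 | 38–52 |
| 'During' on-treatment time that is pre-pandemic | 52–59% | 35–41% |
| 'Pre' on-treatment time that is pandemic time | 11–25% | 14–32% |
| Share of all pandemic exposure held by 'pre' | 75–85% | 36–55% |

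**Step 4: attenuation.** If the hazard doubles once the period starts, a group with pandemic share f has an average rate of (1 + f) times baseline. The observed ratio is (1 + f_during)/(1 + f_pre).
- 11 March: from (1 + 0.48)/(1 + 0.25) = 1.18 (1.19 before rounding the shares) to (1 + 0.41)/(1 + 0.11) = 1.27.
- 15 January: from (1 + 0.652)/(1 + 0.315) = 1.26 to (1 + 0.595)/(1 + 0.138) = 1.40.

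Splitting events and time at the period start would return 2.0 under the same constant-hazard assumption.

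**Step 5: precision.** With a 20% event rate and an observed ratio of 1.25, power is about 7% with 12 participants in 'during' and about 10% with 40.

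**The case against.** The strongest reply is that the 3-month look-back is deliberate. The SAP recognises that nobody started treatment during the period and picks out those likely to be on treatment when it began. That is right as far as it goes: 'during' holds about 41–65% pandemic time across scenarios, against 11–32% for 'pre'.

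A reader might infer that the comparison cannot show a pandemic effect at all, or that late starters' events are mostly pre-pandemic everywhere. The documents support neither. The groups do differ in pandemic exposure, so an effect is diluted rather than lost. A pre-pandemic majority appears at or near an 11 March start, but not at 15 January, where the pre-pandemic gap is 12 to 92 days (31 + 30 + 31 for the earliest starter). Relying on the median participant alone would also ignore long-stayers and the 90-day window for immune-related AEs, which lowers the pre-pandemic share.

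Two further objections stand in part. First, an onset-date split has its own confounding: all first doses precede the period, so 'during' time comes later in treatment and early events such as first-infusion reactions fall almost wholly in 'pre'. That argues for showing results by time since first dose and for keeping the existing display beside the new one. Second, the stakes are limited. The analysis is descriptive, has no decision rule, and sits alongside AE listings with dates and reports of COVID-19-related deviations and missed visits.

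**Conclusion.** The point holds in a bounded form. Grouping by start date alone misclassifies events in both directions and attenuates the only planned comparison for the indirect effect. A true doubling of hazard would show as about 1.2 to 1.4, and where the period starts near 11 March the 'during' group would be small. A near-null plot should not be read as reassurance, nor should a small difference be attributed to the pandemic without allowing for enrolment cohort and time on treatment.

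The 24-day window and the 68 to 91 days follow directly from the SAP's dates for an 11 March start. The person-time shares and ratios depend on assumed accrual, duration shape, a constant hazard within each period and country dates, and on a median borrowed from another study. This is a supportive safety analysis; the primary ORR test is untouched.

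**What to change.** In SAP 9 (Table 4, safety with time window) and SAP 15.1.1, add an analysis that:

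1. splits each participant's on-treatment time at the country's COVID-19 start date, using last dose plus 30 days, or plus 90 days for immune-related AEs;
2. assigns each TEAE and AESI to 'pre' or 'during' by onset date;
3. reports exposure-adjusted rates (events, or participants with a first event, per participant-month at risk) and their difference with a confidence interval;
4. shows these by time since first dose, for example up to 12 weeks and after.

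Base any statement on the indirect effect on this analysis. The start-date display may stay as a secondary description, labelled as a comparison of enrolment cohorts, with the 'pre' row reworded to say more than 3 months before the period.

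Cost: SAP wording and modest programming, since AE onset dates, dosing dates and country start dates are already held or specified. Early-treatment 'during' cells will be sparse, and some confounding by time on treatment will remain.

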## 15.1.2 Adverse Events Leading to Study Intervention Discontinuation

Frequency tables summarizing the following actions taken with study treatment will be presented by PT and primary SOC in alphabetical order:

- TEAEs leading to temporary drug interruption
- Related TEAEs leading to temporary drug interruption
- TEAEs leading to permanent treatment discontinuation
- Related TEAEs leading to permanent treatment discontinuation
- TEAEs leading to infusion rate reduction
- Related TEAEs leading to infusion rate reduction

In addition, the incidences for above items will be summarized in an overview table.

The listing of TEAEs leading to permanent treatment discontinuation will also be provided with the relevant information.

## 15.2 Deaths, Other Serious Adverse Events, and Other Significant Adverse Events

### 15.2.1 Deaths

All deaths, deaths within 30 days after last dose of study treatment (in case of re-initiated participants, the last dose will be the last dose of the re-initiation phase), death within 60 days after first dose of study treatment (for all participants, the first dose will be the first dose of the first treatment phase) as well as the primary reason for death will be tabulated based on information from the “Death” eCRF pages.

The following summaries will be provided:

- Number of deaths (including deaths during re-initiation phase)
- Number of deaths within 30 days after last dose of study treatment
- Number of deaths within 60 days after first dose of study treatment
- Primary Reason for Death
  - Progressive disease and/or disease related condition
  - Event unrelated to study treatment
  - Event related to study treatment
  - Unknown

In addition, date and cause of death will be provided in an individual participant data listing together with following dosing information: participant identifier, age, sex, race, date of first/last

study intervention, number of infusions, day relative to the first and the last infusion, autopsy (Y/N/U), AEs with fatal outcome (list preferred terms of AEs with outcome=Fatal, as well as Grade 5 or Serious resulting in death), flag for death within 30 days of last dose of study treatment and flag for death within 60 days of first dose of study treatment.

### 15.2.2 Serious Adverse Events

The number of participants with serious AEs (SAEs) will be described by SOC and PT:

- SAEs
- Related SAEs

Bar charts presenting SAEs and related SAEs of the most frequent PT (at least 5%) will be displayed by worst grade and PT.

Listing of SAEs will also be provided (see description of listing in Section 15.1.1).

### 15.2.3 Bleeding Events

Bleeding events of interest are the preferred terms belonging to the MedDRA SMQ Haemorrhage terms (excluding laboratory terms).

Bleeding events and study drug related bleeding events will be summarized in a frequency table presenting SOC and PT sorted by alphabetical order. The worst grade per participant, per SOC and per PT will be reported:

- Any grade (including missing grade)
- Grade 1
- Grade 2
- Grade 3
- Grade 4
- Grade 5

### 15.2.4 Adverse Events of Special Interest

#### 15.2.4.1 Infusion-Related Reaction including Hypersensitivity

Infusion-Related Reactions (IRRs) are defined as adverse events with PTs according to a pre-specified MedDRA search list, and are divided into two subcategories: “Reactions” and “signs and symptoms” based on criteria on the timely relationship as detailed below:

**Reactions of IRR:** should be considered when onset is on the day of infusion (during or after the infusion) or the day after the infusion (irrespective of resolution date) for any infusion-related

reaction, drug hypersensitivity, anaphylactic reaction, hypersensitivity and/or Type 1 hypersensitivity.

**Signs and symptoms of IRRs and hypersensitivity/allergic reactions:** should be considered when onset is on the day of infusion (during or after the infusion) and resolved completely with the end date on the same day of the infusion or the day after for any of the following: pyrexia, chills, flushing, hypotension, dyspnea, wheezing, back pain, abdominal pain and urticaria.

IRR, overall and by subcategories, will be summarized by the following variables:

- Number of participants with at least one IRR by the worst NCI-CTCAE toxicity grade (grade 1/ grade 2/ grade 3/ grade 4/ grade 5/ missing grade)
- Number of participants with IRR leading to permanent treatment discontinuation
- Number of participants with IRR leading to infusion rate reduction
- Time related to first onset (infusion 1/ infusion 2/ infusion 3/ infusion 4 or later). The events should be assigned to the actual drug infusions that the participant received, not to the planned dates. An IRR is assigned to a drug infusion if its onset is at the same date (but not before dosing when time is recorded) or the following day of drug infusion.

When at least 10 participants will have received premedication for the first infusion and respectively at least 10 participants will have received the first study medication without premedication, results will also be split by premedication (Y/N) subgroups.

The frequency table of IRR AEs by worst grade, SOC, and PT will also be provided.

The listing of IRRs will be provided with the relevant information (see description of listing in Section 15.1.1). One additional listing will display the study drug administration details together with the infusion-related adverse event including administration date (day) /time, reason for modification, type of modification, modification start time, use of pre-medication, IRR AE Preferred Term, IRR AE grade, IRR AE start day /stop day, IRR AE time related to infusion.

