#### Objectives and Endpoints:

Objectives	Endpoints (Outcome Measures)
Primary	
• To evaluate clinical efficacy of M7824 based on ORR	• Confirmed objective response (OR) according to Response Evaluation Criteria in Solid Tumors Version 1.1 (RECIST 1.1) assessed by IRC
Secondary	
• To evaluate clinical efficacy of M7824 based on duration of response (DOR)	• DOR assessed from complete response (CR) or partial response (PR) until progression of disease (PD), death, or last tumor assessment assessed by IRC
• To evaluate clinical efficacy of M7824 based on durable response rate (DRR)	• Durable response of at least 6 months according to RECIST 1.1 assessed by IRC
• To evaluate clinical safety of M7824	• Occurrence of treatment-emergent adverse events (TEAEs) and treatment-related adverse events (AEs), including adverse events of special interest (AESIs)

Objectives	Endpoints (Outcome Measures)
• To evaluate clinical efficacy based on progression-free survival (PFS)	• PFS according to RECIST 1.1 assessed by IRC
• To evaluate ORR, DOR, DRR and PFS by Investigator read	• OR, DOR, DRR, and PFS according to RECIST 1.1 assessed by Investigator read
• To evaluate clinical efficacy based on overall survival (OS)	• OS
• To characterize the pharmacokinetic (PK) profile of M7824	• The concentration observed immediately at the end of infusion ( $C_{EOI}$ ) of M7824 • The concentration observed immediately before next dosing (corresponding to pre-dose or trough concentration [ $C_{trough}$ ] for multiple dosing) of M7824
• To characterize the immunogenicity of M7824	• Immunogenicity of M7824 as measured by antidrug antibody (ADA) assay, from Screening through 12 weeks ( $\pm 2$ weeks) after last treatment
• To evaluate clinical efficacy of M7824 based on ORR, DOR, and DRR according to PD-L1 expression and microsatellite instability (MSI) status retrospectively	• Confirmed OR according to RECIST 1.1 assessed by IRC according to PD-L1 expression and MSI status • DOR and durable response of at least 6 months according to RECIST 1.1 assessed by IRC according to PD-L1 expression and MSI status

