#### 6.9.1

### Infusion-Related Reactions Including Hypersensitivity

Infusion-related reactions, including hypersensitivity, are defined in this section. Infusion-related reactions are AESIs and identified risks for M7824.

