#### Infusion-Related Reactions

Infusion-related reactions are defined as any signs or symptoms experienced by participants during the infusion of pharmacologic or biologic agents or any event occurring during or within 1 day of study intervention administration. They are identified based on a list of Medical Dictionary for Regulatory Activities (MedDRA) preferred terms and criteria on the timely relationship to an infusion. Events are divided into reactions versus signs and symptoms:

- Reactions are considered when onset is on the day of infusion (during or after the infusion) or the day after the infusion (irrespective of resolution date) for IRR, drug hypersensitivity, anaphylactic reaction, hypersensitivity, and type 1 hypersensitivity.
- Signs and symptoms of IRRs and hypersensitivity/allergic reactions are considered when onset is on the day of infusion (during or after the infusion) and resolved completely with the end date within 2 days after onset of (but not limited to) pyrexia, chills, flushing, hypotension, dyspnea, wheezing, back pain, abdominal pain, and urticaria.

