## Changes to the Planned Analyses in the Clinical Study Protocol

The statistical methods as described in the protocol were adopted. There are no changes to the planned analyses.

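### For infusion-reaction signs and symptoms, the SAP's end-date window is one day shorter than the protocol's, and the difference is not declared

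*SAP*

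**What the plan says.** Protocol section 6.9.1 states that "Infusion-related reactions are AESIs and identified risks for M7824". It identifies them from a MedDRA preferred-term list together with "criteria on the timely relationship to an infusion", and splits them into two subcategories.

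- *Reactions* (the infusion-related reaction, anaphylaxis and hypersensitivity terms) need onset on the infusion day or the day after. The date of resolution does not matter.
- *Signs and symptoms* need onset on the infusion day. The protocol also requires that they have "resolved completely with the end date within 2 days after onset of (but not limited to) pyrexia, chills, flushing" and six further named symptoms.

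SAP section 15.2.4.1 keeps the same two subcategories and a pre-specified MedDRA search list. Its *Reactions* rule matches the protocol's in substance. For *signs and symptoms* it keeps the infusion-day onset but requires that the event "resolved completely with the end date on the same day of the infusion or the day after for any of the following", followed by the same nine symptoms.

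SAP section 7 says that the protocol's statistical methods were adopted and adds: "There are no changes to the planned analyses".

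**The concern.** The timing rule decides which events are IRRs, so a different rule gives a different set of events and not just a different display. Adverse events of special interest form part of the secondary safety endpoint (protocol section 3), and protocol section 9.4.2 plans a summary of their incidence.

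In SAP section 15.2.4.1 the same set of events feeds the IRR summaries overall and by subcategory: worst grade, permanent discontinuation, infusion-rate reduction, infusion of first onset, and the table by grade, system organ class and preferred term. If the SAP is programmed as written, these tables rest on a narrower definition than the protocol's. Someone who relies on SAP section 7 would not know that.

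**Working it through.** No figure in the plan needs reproducing. The check compares two definitions.

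**Inputs**
- Onset of signs and symptoms: infusion day in both documents (protocol 6.9.1, SAP 15.2.4.1). Call this day 0.
- Protocol end-date rule: within 2 days after onset, read literally as end date − onset date ≤ 2.
- SAP end-date rule: infusion day or the next day. Because onset is on day 0, this is end date − onset date ≤ 1.
- SAP duration convention (section 9): stop − start + 1, used here to test an inclusive reading of the protocol's two days.

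**Events counted, by end day**

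| End day | Protocol, literal (≤ 2) | SAP (≤ 1) | Protocol, inclusive (end − onset + 1 ≤ 2) |
|---|---|---|---|
| 0 | yes | yes | yes |
| +1 | yes | yes | yes |
| +2 | yes | **no** | no |
| +3 or later | no | no | no |

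On the literal reading the accepted end days are {0, 1, 2} in the protocol and {0, 1} in the SAP. The SAP set is a strict subset, so for any data:

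SAP count of signs and symptoms = protocol count − (listed symptoms with onset on day 0 and end on day +2) ≤ protocol count.

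The same inequality holds for the overall IRR count, because *Reactions* are defined alike in both documents. A participant leaves the overall count only if every qualifying IRR that he or she had was a symptom ending on day +2. Each such participant changes the rate by 1/141 = 0.7 percentage points at the planned sample size.

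The inequality applies to totals. Single cells of the worst-grade and first-onset tables could move either way: if a participant's earliest IRR is excluded, a later one becomes the first.

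**How an event comes to end on day +2.** SAP section 15.1 joins consecutive records of one event and takes the last end date. A symptom that falls in grade on day +1 and resolves on day +2 is thus one event ending on day +2, which the SAP excludes.

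**Is this a version difference?** The SAP is dated 26 August 2020, before protocol versions 4.0 and 5.0. The logged changes to protocol section 6.9.1 are an added premedication sentence (version 2.0) and a change of risk class (version 5.0). No entry names this window.

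**The case against.** **The windows may coincide.** SAP section 9 counts durations inclusively, so two days from onset could mean the infusion day and the next day, which is the SAP rule. This deserves weight, because it would make the effect zero by definition. But the convention governs computed durations, and the protocol counts days *after* onset, which most naturally means onset + 2. Even if the inclusive meaning was intended, the wording needs settling before programming.

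**The SAP is entitled to supply the detail.** It says that it is based on protocol section 9, and protocol section 9.4.2 leaves further safety details to it. That covers detail, but not a narrower event definition combined with a statement that nothing changed.

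**The consequence is limited.** This stands. *Reactions* have no resolution limit in either document. Only individually coded symptoms ending on day +2 are affected, and they remain in the treatment-emergent tables and the adverse event listings. The safety endpoint is descriptive, with no test attached.

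Four stronger readings are tempting, and the documents do not support them.

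- *The SAP also narrows the symptom list.* The protocol's list is worded as open and the SAP's as closed. But both documents identify IRRs from a MedDRA term list and name the same nine symptoms, and a program must close the list somewhere.
- *Sites classify events one way and the analysis another.* Protocol section 6.9.1 describes an identification rule based on terms and timing. It does not ask sites to apply this window, and protocol Table 4 acts on grade.
- *The comparison with and without premedication is biased.* The same rule applies to both groups, so the count in each can only stay or fall. The direction of any effect on the contrast is unknown. That split is also produced only if each group has at least 10 participants.
- *The IRR rate is understated by a known amount.* The protocol's 5% incidence (section 2.3) comes from earlier studies, concerns treatment-related IRRs, and does not state its window. It also does not separate *Reactions*, which cannot be lost, from symptoms. It gives no basis for an estimate.

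**Conclusion.** The inconsistency is real and undeclared. Read literally, the SAP's end-date rule for IRR signs and symptoms is one day shorter than the protocol's, so its signs-and-symptoms count and overall IRR count can only be equal or lower. The number of symptoms ending on day +2 appears nowhere in the documents, so the size cannot be computed and may be zero. It would therefore be wrong to say that the SAP under-reports IRRs; it *can* under-report them. The conclusion rests on reading the protocol's window as onset + 2. The primary endpoint is untouched.

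**What to change.** In SAP section 15.2.4.1, replace the end-date condition for signs and symptoms with the protocol's window, written so that it can be programmed without interpretation: onset on the infusion day and an end date no later than onset + 2 days. State that the symptoms are those on the pre-specified MedDRA list.

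If the shorter window is intended, declare and justify it in SAP section 7, and present the IRR summary under both windows.

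The cost is one changed programming condition, or one repeated table. The reported IRR rate may be slightly higher as a result.
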